# 10.3. Analysis Sets

In accordance with guidance from the International Conference of Harmonization of Technical Requirements for Registration of Pharmaceuticals for Human Use (ICH) guideline ICH E9 Statistical Principles for Clinical Trials (ICH, 1998), the following populations of analysis will be used for all statistical analysis:

## 10.3.1. Full Analysis Set

The FAS includes all randomized patients excluding patients affected by the urgent safety measure in May 2018 (ie, patients randomized to the 3 mg Q4W or 6 mg Q8W doses) and is based on the treatment allocated (as randomized). Efficacy and patient reported outcome endpoints for Year 1 will be analyzed using the FAS including patients randomized to fasinumab 1 mg Q4W, fasinumab 1 mg Q8W, naproxen and placebo. For the analyses of fasinumab 1 mg Q8W group comparing to the control groups, only patients concurrently randomized (ie, after Protocol R475-OA-1611 Amendment 5 Global was implemented) will be included.

#### 10.3.2. Modified Full Analysis Set

Due to regional irregularities noted in a parallel phase 3 study that became fully apparent only after unblinding that study, and the concern that the same irregularities would be present in data from similar sites from the same region in this study, the primary and secondary efficacy analyses will be performed on an mFAS. This mFAS is comprised of the FAS excluding patients from the region of concern (Rest of the World stratum). Efficacy and patient-reported outcome endpoints will be analyzed using the mFAS including patients randomized to fasinumab 1 mg Q4W, fasinumab 1 mg Q8W, naproxen, and placebo. For the analysis of fasinumab 1 mg Q8W group comparing to the control groups, only the subset of patients concurrently randomized (ie, after Protocol R475-OA-1611 Amendment 5 Global was implemented) will be included.

## 10.3.3. Per-Protocol Set (PPS)

The per protocol set (PPS) includes all randomized patients from the mFAS who received all protocol-required doses during the 16-week treatment period for the week 16 analysis and who do not have to be excluded due to relevant protocol violations. The PPS will be used to perform sensitivity analyses for the primary and selected secondary endpoints. A list of protocol violations which lead to exclusion from the PPS and corresponding protocol deviation identification number (PDID) will be included in the SAP. For the analysis of fasinumab 1 mg Q8W group comparing to the control groups, only patients concurrently randomized (ie, after Protocol R475-OA-1611 Amendment 5 Global was implemented) will be included.

A PPS using the entire FAS is defined analogously to the above and will be used for performing sensitivity analysis on the entire FAS.

## 10.3.4. Safety Analysis Set

The Year 1 safety analysis set (SAF - Year 1) includes all randomized patients from the FAS who received any study drug; it is based on the treatment received (as treated). Treatment compliance/administration and all clinical safety variables for Year 1 will be analyzed using the SAF - Year 1 including patients randomized to fasinumab 1 mg Q4W, fasinumab 1 mg Q8W, naproxen, and placebo.

The Year 2 safety analysis set (SAF - Year 2) includes all patients who received at least 1 dose of the Year 2 study drug; it is based on the treatment received during Year 2 (as treated). Treatment compliance/administration and all clinical safety variables for Year 2 will be analyzed using this SAF – Year 2.

#### 10.3.5. Urgent Safety Measure Set

The urgent safety measure set (USMS) will include all patients randomized to fasinumab 3 mg Q4W or 6 mg Q8W and is based on the treatment allocated (as randomized). The USMS will be utilized for all analyses of data collected from its included patients.

## 10.3.6. Pharmacokinetic Analysis Set

The PK analysis set includes all treated patients who had at least 1 non-missing drug concentration result following the first dose of study drug. Patients will be analyzed according to the treatment actually received (as treated).

#### 10.3.7. Anti-Drug Antibody Analysis Set

The ADA analysis set includes all treated patients who received any study drug and had at least 1 non-missing ADA result following the first dose of study drug. Patients will be analyzed according to the treatment actually received (as treated).

#### **10.3.8.** The Neutralizing Antibody Set

The NAb analysis set includes all patients who received any study drug and who are negative in the fasinumab ADA assay or with at least 1 non-missing result in the fasinumab NAb assay following the first dose of the study drug. Patients who are ADA negative are set to negative in the NAb analysis set. Patients will be analyzed according to the treatment actually received (as treated).

#### 10.4. Statistical Methods

#### **10.4.1.** Patient Disposition

The following will be provided:

• The total number of screened patients: met the inclusion criteria regarding the target indication and signed the ICF

- The total number of randomized patients: received a randomization number
- The total number of patients in each analysis set
- The total number of patients who discontinued the study, and the reasons for discontinuation
- A listing of patients treated but not randomized, patients randomized but not treated, and patients randomized but not treated as randomized
- A listing of patients prematurely discontinued from treatment, along with reasons for discontinuation

## 10.4.2. Demography and Baseline Characteristics

Baseline demographic, disease characteristics including medical history, and exposure to study drug will be summarized descriptively by treatment group using descriptive statistics. Continuous variables will be summarized with mean, median, SD, minimum, and maximum. For categorical or ordinal data, frequencies and percentages will be displayed for each category.

Details of the statistical methods will be provided in the SAP.

## 10.4.3. Efficacy Analyses

## 10.4.3.1. Primary Efficacy Analysis

The primary efficacy variables will be analyzed using multiple imputation approach with a mixed-effect model for repeated measure (MMRM) based on the mFAS with adjustment for missing data due to lack of efficacy, death or AEs assuming the WOMAC scores would on average return to baseline values. A monotone missing data structure will be achieved using the MCMC option of PROC MI. Data collected after discontinuing treatment up to week 16 will not be used in the primary efficacy analysis, but used in a treatment policy sensitivity analysis. Multiple imputation for the remaining data will be based on the monotone missing data structure of the change from baseline scores using the regression imputation option in PROC MI. The missing data for patients who discontinued treatment due to other reasons will be imputed under missing-at-random assumption. The imputed data for patients discontinued from the study treatment due to lack of efficacy, death or AEs will be centered at the mean baseline value.

Missing data will be imputed 50 times to generate 50 complete data sets. Each imputed data set will be analyzed using the MMRM with terms for baseline score corresponding to the efficacy variable being analyzed, randomization strata (K-L category [2 to 3, or 4], index joint [knee, hip], and geographical region [North America, Europe]), treatment, visit, and treatment-by-visit interaction. The MMRM will be performed using the MIXED procedure in Statistical Analysis System (SAS) with an unstructured covariance matrix to model the within-patient errors. Denominator degrees of freedom will be estimated using Kenward-Roger's approximation. The results from the 50 analyses will be combined using Rubin's formulae (PROC MIANALYZE). The least-squares mean estimates for the mean change from baseline to week 16, as well as the differences of the estimates between fasinumab and placebo, and between fasinumab and naproxen, with their corresponding standard errors, p values and associated 95% confidence intervals, will be provided.

Sensitivity analysis of the treatment policy estimand for the co-primary endpoints will be performed using similar analysis method as the primary efficacy analysis including data collected after discontinuing treatment up to week 16. Sensitivity analysis using a tipping point approach with multiple imputation will be performed to assess the robustness of the results due to data that may be missing not-at-random (MNAR). After each imputation, a fasinumab patient's imputed data will subtract  $\delta$  from the imputed score at each corresponding time point. By progressively increasing  $\delta$ , the sensitivity analysis will explore the tipping point, ie, the  $\delta$  value when the p-value for a treatment comparison is above 0.05. Additional analyses will be performed for the primary and select secondary endpoints using the PPS.

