#### 10. STATISTICAL PLAN

This section provides the basis for the statistical analysis plan (SAP) for the study. The SAP may be revised during the study to accommodate amendments to the clinical study protocol and to make

changes to adapt to unexpected issues in study execution and data that may affect the planned analyses. The final SAP will be issued before the database is locked.

Analysis variables are listed in Section 1.

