## **1. OVERVIEW**

The purpose of the statistical analysis plan (SAP) is to ensure the credibility of the study results by pre-specifying the statistical approaches for the analysis of study data prior to database lock. The SAP is intended to be a comprehensive and detailed description of the strategy and statistical methods to be used in the analysis of data for R475-OA-1611 study as stipulated in Protocol Amendment 8 Global.

This plan may be revised during the study to accommodate protocol amendments and/or to make changes to adapt to unexpected issues in study execution and/or data that affect planned analyses. These revisions will be based on blinded review of the study and data, and a final plan will be issued prior to data lock and before code breaking.

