### **1.2.3. Modifications from the Statistical Section in the Final Protocol**

There are no modifications from what is defined and specified in the statistical section of the final protocol.

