### Tipping Point Analysis

Sensitivity analysis using a tipping point approach with multiple imputation will be performed to assess the robustness of the results due to data that may be missing not-at-random (MNAR).

This approach will introduce a sensitivity parameter,  $\delta$ . Estimations will be performed using multiple imputation methodology. Missing data up to week 52 timepoint will be imputed 50 times to generate 50 complete datasets by using SAS procedure PROC MI for each  $\delta$  following the 2 steps below:

- Step 1: The monotone missing pattern is induced by Markov Chain Monte Carlo (MCMC) method in MI procedure using seed number 4751611. If a randomly imputed score is imputed outside the range of the WOMAC subscale score of 0-10, then the algorithm will continue to randomly impute scores until one within the range of 0-10 is obtained.
- Step 2: The missing WOMAC subscale scores at visits subsequent to treatment discontinuation will be imputed using the regression method for the monotone pattern with seed number 4751611 and adjustment for covariates including treatment groups, randomization strata strata (K-L category [2 to 3, or 4], index joint [knee, hip], and geographical region [Europe, North America]), baseline WOMAC subscale score and all WOMAC subscale scores at preceding visits. Scores that are imputed outside the range of the WOMAC subscale will be addressed in the same manner as in step 1.
- Step 3: For missing data because of permanent study treatment discontinuation due to adverse events, death or lack of efficacy,  $\delta$  will be added to the imputed values ( $\delta = 0$  corresponds to the MAR assumption).

Each imputed data set will be analyzed using a MMRM model with terms for baseline WOMAC subscale score corresponding to the efficacy variable being analyzed, randomization strata (K-L category [2 to 3, or 4], index joint [knee, hip], and geographical region [Europe, North America]), treatment, visit, and treatment-by-visit interaction as fixed effects. For each  $\delta$  the SAS MIANALYZE procedure will be used to generate valid statistical inferences by combining results from the 50 analyses using Rubin's formula. By progressively increasing  $\delta$ , the sensitivity analysis will explore the tipping points, e.g.,  $\delta$  value when the p-value for a treatment comparison is above 0.025 or 0.05. Results will be then summarized using summary tables and graphs.

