### 5.7.2. Subgroup Analysis

Descriptive analyses by treatment group will be performed on both raw and change from baseline values for each visit for the WOMAC pain subscale score and physical function subscale scores to summarize the treatment effects across subpopulations defined by the following baseline characteristics:

- K-L category [2 to 3, or 4]
- Index joint [Knee, Hip]
- Region [Europe, North America]
- Age group [ $< 65$ , 65-74,  $\geq 75$  years]
- Sex [Male, Female]
- Weight group [ $<$  median baseline weight,  $\geq$  median baseline weight kg]
- BMI group [ $\leq$  median baseline BMI,  $>$  median baseline BMI]
- Flare status [Flare, Non-Flare] where flare patients are defined as patients who experience a  $\geq 1$  point increase in WOMAC pain scores from the Screening to the Baseline Visit.

An MMRM model analogous to that used for the primary analysis will be constructed, also including terms for subgroup and subgroup-by-treatment, subgroup-by-visit and subgroup-by-treatment-by-visit interactions as fixed effects. Multiple imputation will not be performed for the subgroup analyses. In addition to the actual change from baseline values, their LS means, differences of LS Means between treatment groups and corresponding 95% CIs within each subgroup at each visit will be presented. The p-value corresponding to the overall subgroup-by-treatment interaction will be supplied. Forest plots for the subgroup analyses will also be provided.

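### Protocol 10.4.3.1's tipping-point rule shifts fasinumab's imputed WOMAC scores in the favourable direction; the SAP reverses the sign but names no arm and declares no change

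*Protocol*

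**What the plan says.** **Protocol 10.4.3.1.** In the tipping-point analysis, "After each imputation, a fasinumab patient's imputed data will subtract" delta at each time point. Delta is then increased step by step, and the tipping point is the "value when the p-value for a treatment comparison is above 0.05". The sentence names fasinumab patients and does not restrict the shift by reason for discontinuation.

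**SAP 5.7.1, Tipping Point Analysis, Step 3.** "For missing data because of permanent study treatment discontinuation due to adverse events, death or lack of efficacy", delta is added to the imputed values, and delta of zero corresponds to missing at random (MAR). No treatment arm is named. Tipping points are given by example as the delta "value when the p-value for a treatment comparison is above 0.025 or 0.05".

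**SAP 1.2.3.** "There are no modifications from what is defined and specified in the statistical section of the final protocol".

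**Direction of the scale.** SAP 5.7.2 defines a flare as at least a 1-"point increase in WOMAC pain scores from the Screening to the Baseline Visit". Protocol 6.2.1, criterion 5, sets moderate-to-severe pain at a score of 4 or more. Higher is worse.

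**Which text leads.** Protocol section 10 says of itself: "This section provides the basis for the statistical analysis plan (SAP) for the study". SAP section 1 describes the SAP as "a comprehensive and detailed description of the strategy and statistical methods".

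**The concern.** A tipping-point analysis should make the missing outcomes of the treated arm progressively worse and report how much worse they must be before significance is lost. The protocol makes them progressively better. For a result that favours fasinumab, p can then only fall, and the output would look like growing robustness.

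The SAP has the adverse direction but leaves out the arm. The only document that names the arm therefore has the wrong sign, and the document with the right sign names no arm. If delta went to every arm in equal shares, it would cancel from the mean difference.

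This is the only planned delta-adjusted analysis. The other two sensitivity analyses in SAP 5.7.1 address different questions: the treatment-policy analysis uses observed off-treatment data, and the per-protocol set requires all doses to week 16 and a week-16 WOMAC assessment.

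**Working it through.** **1. Direction.** Let the difference be fasinumab minus placebo in mean change, so that benefit is negative. Imputing change from baseline rather than the raw score does not reverse the sign. Step 3 of the SAP's primary analysis returns dropouts to baseline by subtracting the mean change, so change is post-baseline minus baseline and improvement is negative.

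**2. Inputs.** Protocol 10.2 and SAP 2.2 give:
- 840 vs 280 patients (Q4W vs placebo) and 600 vs 200 (Q8W vs placebo)
- a Q4W difference of 1.1 with SD 2.4
- a Q8W effect at 80% of that: 0.8 × 1.1 = 0.88
- 15% dropout to week 16 and two-sided alpha 0.025

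The share of patients whose scores are shifted is not given. I assume 5%, 10% and 15%. The last equals total planned week-16 dropout, so it is an upper bound for SAP Step 3.

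**3. The plan's own power, as a check.** Power = Φ(ES/√(1/n₁+1/n₀) − 2.241), with sizes reduced by 15%.
- Q4W: n = 714 and 238; 0.46/0.0748 = 6.15; power above 99.9% (plan: at least 99%).
- Q8W: n = 510 and 170; 0.368/0.0886 = 4.16; Φ(1.91) = 97.2% (plan: 97%).

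**4. Effect of the shift.** With shifted shares p_F and p_P:

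difference(δ) = −D + s·δ·(p_F − p_P)

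- protocol: s = −1, p_P = 0
- fasinumab only: s = +1, p_P = 0
- all arms, equal shares: s = +1, p_P = p_F

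Each arm's variance is 2.4² + p(1−p)δ². The SE uses arm-specific or pooled variances, which gives the ranges below. Delta runs from 0 to 10 without capping, and between-imputation variance is ignored.

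At δ = 0, Q4W has SE 2.4·√(1/840+1/280) = 0.166 and z = −6.6. Q8W has SE 0.196 and z = −4.5.

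Worked example (Q4W, 15%, fasinumab only, δ = 5.03, arm-specific variance): difference = −1.1 + 0.15 × 5.03 = −0.346; fasinumab variance = 5.76 + 0.1275 × 25.3 = 8.99; SE = √(8.99/840 + 5.76/280) = 0.177; z = −1.95, just past −1.96.

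| Rule (p>0.05) | Q4W, 15% | Q8W, 15% | Q4W, 10% | Q8W, 10% |
|---|---|---|---|---|
| Protocol (subtract, fasinumab) | never | never | never | never |
| Add, fasinumab only | 4.8–5.0 | 3.1–3.2 | 6.9–7.4 | 4.5–4.8 |
| Add, all arms, equal shares | never | never | never | never |

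Under the protocol rule the weakest z is always the one at δ = 0. At 15% and δ = 10 the Q4W difference is −1.1 − 1.5 = −2.6 and z lies between −9.6 and −12.6. At 5% shifted, adding to fasinumab only does not tip Q4W anywhere on 0 to 10. For p>0.025 at 15%, fasinumab-only tips at 4.5–4.7 (Q4W) and 2.8–2.9 (Q8W).

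With unequal shares the all-arms reading can even help fasinumab: with 10% shifted on fasinumab and 20% on placebo, δ = 10 gives −1.1 + 10 × (0.10 − 0.20) = −2.1.

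**5. Version gap.** The SAP is written to Amendment 8. Amendment 9's list of changed sections does not include 10.4.3.1, so a later amendment does not explain the mismatch. The SAP passage also announces two steps and then lists three, which suggests that the text was not reconciled.

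**The case against.** The strongest reply is that the SAP is the detailed plan, it already adds delta, and the protocol's harmful direction would not be run. That stands for the sign. It does not supply the arm.

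The arm can be inferred: the protocol says fasinumab, and SAP 1.2.3 says nothing was modified. That is a reasonable reading. But it takes the arm from a sentence whose sign the SAP has just reversed, so the no-modification statement cannot carry much weight.

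The scope and threshold differences are weaker, and I accept most of this. The protocol's rule concerns data that may be missing not at random, and its primary analysis treats only adverse-event, death and lack-of-efficacy dropouts that way, so the SAP can be read as specifying the protocol. The SAP's thresholds are examples that include 0.05, and both can be reported. These are differences to declare rather than contradictions.

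The primary analysis also already applies a return-to-baseline imputation to these same dropouts. That stands as a safeguard. The SAP's tipping analysis, however, starts from MAR for them at delta zero, and it leaves dropouts for other reasons at MAR throughout.

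Finally, 15% is an upper bound, and shifts near 10 on a 0 to 10 scale give impossible scores. This affects the size of the tipping delta, not the direction.

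**Conclusion.** The concern holds as a defect of wording and consistency in a supportive analysis. As written, the protocol rule cannot tip a favourable fasinumab result, whatever share of patients is shifted. The SAP corrects the sign without naming the arm, and the change is undeclared. The primary test is unaffected.

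The tipping values rest on planned FAS sizes and effects, assumed shares, no capping and a simplified SE. They show that the choice of arm decides whether there is any tipping point at all; they do not predict the trial's result.

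A reader might infer more than the documents support:
- **That the analysis will be run in the wrong direction.** The SAP adds delta.
- **That the SAP intends to shift all arms.** It is silent; all arms is only the literal reading.
- **That the protocol rule shows robustness whatever the data.** This is true only when the estimate favours fasinumab. If fasinumab looked worse, subtraction could tip the result.
- **That a tipping delta for the mFAS can be derived from the SAP's 42% and 46% power for Q8W.** The mFAS arm sizes and effects are not given. Power below 50% also means the expected Q8W result would not reach the stated 0.01 level, so there would be no significant result at that level to tip.

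**What to change.** 1. In protocol 10.4.3.1, correct the sign so that delta worsens fasinumab's imputed scores.
2. In SAP 5.7.1, Step 3, state that delta of zero or more is added to fasinumab patients' imputed scores, with control arms unshifted.
3. Make the two documents agree on which discontinuations are shifted and on the p-value threshold or thresholds.
4. Declare the differences in SAP 1.2.3.

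Optional additions are a two-way grid with a separate delta per arm, a further run that shifts all imputed fasinumab data, and a statement on whether shifted scores are capped at 10.

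The cost is a few lines of text and matching program code. No new data are needed.

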## 10.4.3.2. Secondary Efficacy Analysis

For analysis of continuous secondary endpoints at fixed timepoints (ie, week 16 and week 44), the analysis method will be the same as that used for the primary variables. For the analysis of secondary endpoints involving the averaging over several visits (see endpoints 12 to 15 in Section 4.2.2), analysis will be performed using a multiple imputation approach with an ANCOVA model based on the mFAS with adjustment for missing data performed in the same manner as was done for the primary endpoint. For analysis of categorical variables in secondary endpoints, eg, proportions of patients with ≥30% improvement in the WOMAC pain subscale scores at week 16, the Cochran Mantel Haenszel approach will be used based on the mFAS, stratifiying by the randomization strata (K-L category [2 to 3, or 4], index joint [knee, hip], and geographical region [North America, Europe]). Missing data will be considered as non-response.

For Year 2 analysis, the efficacy and PRO endpoints collected will be summarized descriptively.

